6.5.6 Month 24 Telephone Contact

A Month 24 telephone contact will be made to assess current medications, as well as morbidity and mortality in study subjects.

6.5.7 Follow-up Windows

The timeline for follow up will initiate with the day of SPI (Day 0). The time windows for each of the subsequent follow up visits will be as follows:

1. The 1-week visit will be 7 ± 3 days (from day of SPI).
2. The 1-month visit will be at 30 ± 7 days.
3. The 6-month visit will be at 180 ± 30 days.
4. The 12-month visit will be at 365 ± 30 days.
5. The 24-month phone call will be at 730 ± 30 days.

6.5.8 Lost to Follow-up

Randomized subjects will be followed for up to two years. Subjects will be considered lost to follow-up after 3 consecutive failed telephone contacts AND one certified letter returned to the site. Contact attempts will be documented in the subject's study chart.

6.6 Collection of Endpoints***6.6.1 Six-minute Walk Test (6MWT)***

6MWTs will be performed to assess functional capacity. Subjects will perform a 6MWT during baseline and at 6 and 12 months. See Protocol Manual of Operations for acquisition details.

To minimize external sources of test-retest variability, 6MWTs will be administered by testers blinded to treatment arm. Two tests will be done at each of the 3 visits (baseline, 6, and 12 months) separated by at least 30 minutes. If the variance between test 1 and test 2 for total distance walked is $>10\%$, a third test will be done. The tests will be done at consistent intervals.

6.6.2 Minnesota Living with Heart Failure Questionnaire (MLHFQ)

The subjects' quality of life will be assessed with the MLHFQ during baseline and at 6, and 12 months. The questionnaire includes details of subjects' symptoms specifically related to functional status and development of HF.

6.6.3 Cardiac Magnetic Resonance Imaging (cMRI) Evaluation

Cardiac MRI is a new diagnostic modality that provides superior assessment of the cardiac function, myocardial scar size measurement, and myocardial perfusion evaluation. Steady state free precession (SSFP) cardiac MR imaging will provide valuable information regarding cardiac anatomy and will assess the myocardium, including myocardial mass and zones of acute infarction. Cine MRI will also be performed on study patients and it is used to evaluate left and right ventricular function and size, and valvular and shunt lesions. Contrast-enhanced MRI will also be used to assess myocardial viability and scar quantification.

In addition to these more traditional cardiac MR techniques, we will be using T1 myocardial mapping techniques (at centers which have this capability and are qualified by the MRI Core Lab) to help garner a more complete picture of the myocardial condition. Recently, T1 mapping has been shown to effectively demonstrate fibrotic changes in myriad pathologic conditions¹¹⁴⁻¹¹⁶. While the delayed gadolinium enhancement is very sensitive to small areas of regional fibrosis, the method is dependent on the comparison to the signal from “normal myocardial” reference areas. In patients with more diffuse fibrosis (such as those with AIC), T1 mapping will be an essential adjunctive tool. Preliminary studies involving AIC and T1 mapping are promising¹¹⁷.

In addition to the evaluation of myocardial fibrosis, the utility of cardiac MR studies for gauging functional indices is also quite robust. However, while LVEF has been used as a “gold standard” of therapeutic response, it may lack the sensitivity required to measure subtler, yet clinically relevant changes. Conceptually, this correlation between decreased strain and clinical events has been well described. One seminal study included 147 patients with heart failure with LVEF \leq 45% (mean age, 64 \pm 14 years; 74% men; mean LVEF, 29.9 \pm 8.9%)¹¹⁹. Clinical events were observed in 20% of patients during the 12-month follow-up period and global longitudinal strain was shown to have the highest prognostic value over conventional EF measurements with an area under the curve of 0.83 using a cutoff of -7%¹¹⁹. Specifically, in chemotherapy-induced cardiomyopathies, strain has been shown to have greater sensitivity and have similar predictive value¹²⁰. Hence, using cardiac MR studies to measure these more sensitive indices of function may allow for a more informative and conclusive study of cell therapy mechanisms and benefits in this setting. Tagged MRI will be performed, and global and regional myocardial strains and strain rates will be computed using the harmonic phase method.

This information, obtained before and after study product injection, will be crucial in estimating the benefit gained by injecting stem cells as well as evaluating the potential side effects.

Cardiac MRI will be performed in all patients at baseline and at 6 and 12 months after SPI. See MRI Core Lab Manual of Operations for acquisition details.

Guidance to the Principal Investigator: MRI was selected as the imaging modality for endpoint collection due to its excellent capability to identify scar and changes in LV function. The resolution of the imaging is such that it can also detect LV thrombi that may not otherwise be found using the standard echocardiogram. This includes many old, small, organized, endothelialized, mural thrombi that may or may not rise to the level of clinical significance.

The MRI core lab provides the statement of any findings and also provides to the clinical team a weblink to the actual MRI images with instruction on the location of the finding(s) (i.e. which series/views will highlight it for their review). This allows the PI/interventionalist at the center to readily identify the location, view the images, and request additional info if needed. All studies

CONFIDENTIAL AND PROPRIETARY

are reviewed by the local radiologist for clinical findings for the PI's consideration before enrollment.

Identification and clinical evaluation of LV thrombus: The MRI core lab will provide their interpretation about the presence of a thrombus to the local center. The MRI core lab will differentiate between the LV thrombi that meet the definition of an exclusion on the one hand from the smaller LV thrombi that would likely not appear on echo. The MRI core lab will describe the latter by stating, "*cannot rule out small LV thrombus*". For these, it will then be up to the site study Principal Investigator and the interventionalist to follow up in making the determination of clinical significance of any finding and whether (and when) they would proceed with study procedures. This leaves the decision to proceed in the presence of the smaller LV thrombi identified by MRI in the hands of the site study PI based on their assessment of clinical significance. If they proceed, documentation of that determination must be included in the participant's chart.

6.6.3.1 Performance of MR examinations in subjects with implantable cardiac devices (ICD/pacemakers)

The presence of a pacemaker or implanted defibrillator device is not a contraindication to MRI scanning^{121,122}.

The procedures use are based upon the safety recommendations as listed in “Safety of Magnetic Resonance Imaging in Subjects With Cardiovascular Devices: An American Heart Association Scientific Statement”¹²¹. In particular, the recommendations include:

1. Written and verbal informed consent is obtained. Specific risks are documented, including
 - a. pacemaker/ICD dysfunction and/or damage
 - b. arrhythmia
 - c. device dislodgement
 - d. thermal injury
 - e. death
2. There is direct involvement of a cardiologist with pacemaker/ICD expertise, to oversee pre-scan device measurements, device changes including therapy (ICD) disabling for the duration of the scan, and post-scan measurements and re-enabling of therapy and other device parameters.
3. Advanced Cardiovascular Life Support (ACLS) trained personnel and a "crash cart," including defibrillator, are available throughout the procedure to address an adverse event.
4. Maintenance of visual and voice contact with the subject throughout the procedure.
5. At all times during which the device is disabled, continuous ECG telemetry and pulse oximetry, blood pressure measurements every 5 minutes, and symptoms are monitored including throughout the scan.

Regarding specific implanted device parameter measurements and programming changes, protocols of Johns Hopkins University¹²³ is used as follows:

1. Exclusion of subjects whose devices were manufactured before 2000
2. Exclusion of subjects with nontransvenous epicardial, or abandoned (capped) leads
3. Exclusion of pacemaker-dependent subjects with ICDs
4. ICD therapies are disabled during the study to avoid unwarranted anti-tachycardia pacing or shocks

CONFIDENTIAL AND PROPRIETARY

5. Limitation of the estimated whole-body averaged SAR to <2.0 W/kg for MR scan acquisition
6. Exclusion of subjects with leads implanted less than six weeks prior to study enrollment

As a part of the training process, experienced personnel with large volume experience in MR imaging patients with pacemakers and ICDs will oversee the initial cases at each site until adequate proficiency is reached by each site's imaging staff members.

6.7 Collection of Biospecimens

A central CCTRN biorepository will be utilized in this study. The biorepository will be included in the consent form and subjects will have the option of participating in the sample donation. Participation in the study does not equate with participation in donating to the biorepository; subjects can decline the biorepository donation and still participate in the overall trial.

The goal of this biorepository is three-fold: 1) to provide storage of critical biomaterials (i.e., subject peripheral blood and donor allo-MSC product) 2) to provide long-term integrity (up to 10 years) of these biospecimens and products, and 3) to provide management of samples for ancillary studies of immunologic, immunohistochemical, cellular, and molecular analyses of donor allo-MSC product and subject serum samples; as well as phenotypic and functional analyses of cells and plasma samples with an aim toward gaining insight into diagnostics of disease progression and prognostics of successful intervention.

These biomaterials will be used for research purposes only (not for profit), will be stored without personal identifying information, and will be shared with approved researchers who will conduct studies to improve the understanding of the effects of cell therapies. Biomaterials will be destroyed after 10 years.

6.7.1 Peripheral Blood

Twenty ml of peripheral blood will be collected on Day 0 (day of injection, before sedation for SPI procedure), Day 1 (within 24 hours after SPI), Week 1, 1 month, and 6 months. This blood will be sent to the CCTRN biorepository per core lab SOP.

6.7.2 Allo-MSC Allografts

A sample of the allo-MSC cell bank will be provided to the CCTRN biorepository for additional characterization studies.

6.7.3 Explanted Hearts

Included in the informed consent is a request for the explanted heart in cases of transplant or in the event of the participant's death. With appropriate consent, the explanted heart will be sent to the CCTRN biorepository for further study.

All surplus biospecimens (bone marrow and blood) will be cryopreserved up to 10 years.

7.0 EVENT MONITORING AND REPORTING

The safety monitoring program is a comprehensive, data driven program that provides ongoing capture and analyses of safety data and issues timely notifications, event specific reports, and scheduled cumulative trial reports of safety issues to appropriate study personnel, the NHLBI Program Director, the Data and Safety and Monitoring Board (DSMB), and the Food and Drug Administration (FDA). The program complies with applicable U.S. law, regulations, and guidance.

CONFIDENTIAL AND PROPRIETARY

7.1 Definitions Related to Adverse Events

The following definitions arise from recently modified FDA reporting regulations and International Conference on Harmonization (ICH) guidelines for use in this study:

7.1.1 Adverse Events (AEs)

An adverse event (AE) is defined as any untoward medical occurrence associated with the use of a drug in humans, whether or not considered drug related. An AE can be any unfavorable and unintended sign (including an abnormal laboratory finding), symptom, or disease temporally associated with the study. The event does not need to have a causal relationship with treatment.

7.1.2 Suspected Adverse Reaction (SARs)

A suspected adverse reaction (SAR) is defined as any adverse event for which there is a reasonable possibility that the drug caused the adverse event. For the purposes of IND safety reporting, "reasonable possibility" means there is evidence to suggest a causal relationship between the study product/procedures and the adverse event.

7.1.3 Serious Adverse Events (SAEs) or Serious Suspected Adverse Reaction (SSAR)

A serious adverse event (SAE) or serious suspected adverse reaction (SSAR) is defined as an AE/SAR which, in the view of the Investigator or Sponsor, results in: 1) Death; 2) a life-threatening event (i.e. an event in which the subject was at risk of death at the time of the event; it does not refer to an event which hypothetically might have caused death if it were more severe); 3) inpatient hospitalization of > 24 hours or prolongation of existing hospitalization; 4) a significant disability/incapacity; or 5) a congenital anomaly/birth defect. Other important medical events may be considered SAEs/SSARs if, in the opinion of the Investigator or DCC, they jeopardize the subject or require intervention to prevent one of the other outcomes listed above.

7.2 Role of Abnormal Test Findings and Hospitalizations in Classifying an Event

7.2.1 Abnormal Test Findings

If a test result is associated with accompanying symptoms, and/or the test result requires additional diagnostic testing or medical/surgical intervention, and/or the test result is considered to be an AE/SAR by the Investigator or Sponsor it should be reported as an adverse event.

NOTE: Merely repeating an abnormal test, in the absence of any of the above conditions, does not constitute an AE/SAR. Any abnormal test result that is determined to be an error does not require reporting as an AE/SAR.

7.2.2 Hospitalizations

AE/SARs associated with hospitalization or prolongation of hospitalization are classified as serious. Admission also includes transfer within the hospital to an acute/intensive care unit (e.g., from the cardiac wing to the medical floor for an infection, or from the medical division to the neurologic unit for a stroke).

Hospitalization does not include rehabilitation facilities, hospice facilities, respite care (i.e., caregiver relief), skilled nursing facilities or homes, routine emergency room admissions, or same day surgeries (as outpatient/same day/ambulatory procedures).

Hospitalization or prolongation of hospitalization in the absence of a precipitating, clinical AE/SAR is not in itself an SAE/SSAR.

7.3 Reporting Responsibilities of the Investigator

For all events (AE/SAR and SAE/SSAR), monitoring and reporting to the DCC begins at the time that the subject provides informed consent, which is obtained prior to the subject's participation in the study, i.e., prior to undergoing any study related procedure and/or receiving investigational product, through and including 30 calendar days after the subject completes the 12-month clinic visit. Events should be recorded on the Adverse Event electronic case report form (eCRF). Do not delay the initial reporting of an event in order to obtain resolution or follow up information.

For all events, the Investigator must pursue and obtain adequate information both to determine the severity and causality of the event. For events with a causal relationship to the investigational product, follow-up by the Investigator is required until the event or its sequelae resolve or stabilize at a level acceptable to the Investigator, and the DCC concurs with that assessment.

In the event that the Investigator does not become aware of the occurrence of a SAE/SSAR immediately (i.e., if an outpatient study subject initially seeks treatment elsewhere), the Investigator is to report the event within 24 hours after learning of it and document the time of his/her first awareness of the event.

7.3.1 Severity Assessment

The DCC uses the Common Terminology Criteria for Adverse Events (CTCAE), version 4.0, for detailed descriptions of Severity Grades. The CTCAE schema is classified by body system and event using the MedDRA hierarchy and provides descriptions of events that qualify under each severity rating.

The following table contains general descriptions of Adverse Event Severity Grades.

Please note: Grade 1 (Mild) AE/SARs are not entered in the electronic CRF in the CCTRN database.

Severity Grade	Description
1	Mild. Asymptomatic or mild symptoms; clinical or diagnostic observations only; intervention is not indicated.
2	Moderate. Minimal, local, or non-invasive intervention indicated or limiting activities of daily living (i.e. preparing meals, shopping for groceries/clothes, managing money, using telephone, etc.)
3	Severe or medically significant but not immediately life-threatening. Hospitalization or prolongation of hospitalization indicated OR disabling OR limiting self-care (e.g. bathing, dressing, feeding self, using toilet, taking medications, etc.)
4	Life-threatening consequences; urgent intervention indicated.
5	Death. Death related to adverse event.

Notice that severity and seriousness are different concepts. For example, a headache may be severe (interferes significantly with subject's usual function) but would not be classified as serious unless it met one of the criteria for SAE/SSARs (see section 7.1.3 above).

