20. Coagulopathy (INR > 1.5) not due to a reversible cause (e.g., warfarin and/or Factor Xa inhibitors) (see Section 6.4 re: injection procedure and anticoagulation therapy) *Note: Subjects who cannot be withdrawn from anticoagulation will be excluded.*
21. Presence of LV thrombus (*see guidance in Section 6.6.3*)
22. Presence of a pacemaker and/or ICD generator with any of the following limitations/conditions:
 - manufactured before the year 2000
 - leads implanted < 6 weeks prior to consent
 - non-transvenous epicardial or abandoned leads
 - subcutaneous ICDs
 - leadless pacemakers
 - any other condition that, in the judgment of device-trained staff, would deem an MRI contraindicated
23. Pacemaker-dependence with an ICD (*Note: pacemaker-dependent candidates without an ICD are not excluded*)
24. A cardiac resynchronization therapy (CRT) device implanted < 3 months prior to consent
25. Other MRI contraindications (e.g. patient body habitus incompatible with MRI)
26. An appropriate ICD firing or anti-tachycardia pacing (ATP) for ventricular fibrillation or ventricular tachycardia within 30 days of consent
27. Ventricular tachycardia ≥ 20 consecutive beats without an ICD within 3 months of consent, or symptomatic Mobitz II or higher degree atrioventricular block without a functioning pacemaker within 3 months of consent
28. A history of drug abuse (use of illegal "street" drugs except marijuana, or prescription medications not being used appropriately for a pre-existing medical condition) or alcohol abuse (≥ 5 drinks/day for > 3 months), or documented medical, occupational, or legal problems arising from the use of

alcohol or drugs within the past 24 months

29. Cognitive or language barriers that prohibit obtaining informed consent or any study elements (interpreter permitted)
30. Participation (currently or within the previous 30 days) in a cardiac related investigational therapeutic (including stem cell based therapies) or device trial
31. Pregnancy, lactation, plans to become pregnant in the next 12 months, or is unwilling to use acceptable forms of birth control during study participation
32. Any other condition that, in the judgment of the Investigator or Sponsor, would be a contraindication to enrollment, study product administration, or follow-up

Primary Endpoints

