3.4 Study Endpoints

3.4.1 Safety Assessment

To demonstrate the relative safety of allo-MSCs when compared with placebo, the following safety data will be collected and analyzed by therapy group between baseline and a) 6 months and b) 12 months:

1. Major adverse cardiac events (MACE) including death, hospitalization for worsening heart failure (HF), and/or exacerbation of HF (non-hospitalization)
2. Other significant clinical events including non-fatal stroke, non-fatal myocardial infarction, coronary artery revascularization, ventricular tachycardia/fibrillation, pericardial tamponade, infectious myocarditis, hypersensitivity reaction, neoplasm, or any other potential deleterious late effects detected and corroborated by clinical presentation, laboratory investigations, image analysis, and when necessary with biopsy from suspected target sites in the body
3. All adverse events (AEs) at least grade 2 in severity (see section 7.3.1)

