8.3.2.1 Safety Evaluations

To demonstrate the relative safety of allo-MSCs when compared with placebo, the following analyses will be carried out, and the data tabulated and analyzed by therapy group (Fisher's Exact Test) between baseline and a) 6 months and b) 12 months:

1. Major adverse cardiac events (MACE) including death, hospitalization for worsening heart failure (HF), and/or exacerbation of HF (non-hospitalization)
2. Other significant clinical events including non-fatal stroke, non-fatal myocardial infarction, coronary artery revascularization, ventricular tachycardia/fibrillation, pericardial tamponade, infectious myocarditis, hypersensitivity reaction, neoplasm, or any other potential deleterious late effects detected and corroborated by clinical presentation, laboratory investigations, image analysis, and when necessary with biopsy from suspected target sites in the body
3. All adverse events (AEs) at least grade 2 in severity (see section 7.3.1)

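### Safety items 1 and 2 carry no stated grade floor, but grade 1 events are kept off the one event form described, so mild named events have no stated route into the primary safety tables

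*Combined protocol and SAP*

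**What the plan says.** The Executive Summary lists safety among the primary endpoints. Sections 3.4.1 and 8.3.2.1 give the same three items, analysed by therapy group with Fisher's exact test to 6 and 12 months.

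- Item 1 is MACE: death, hospitalisation for worsening heart failure (HF), or an HF exacerbation without hospitalisation. No grade is stated.
- Item 2 opens with "Other significant clinical events including non-fatal stroke, non-fatal myocardial infarction, coronary artery revascularization, ventricular tachycardia/fibrillation" and continues with "pericardial tamponade, infectious myocarditis, hypersensitivity reaction, neoplasm" and other late effects. No grade is stated.
- Item 3 has an explicit floor: "All adverse events (AEs) at least grade 2 in severity (see section 7.3.1").

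On capture, section 7.3 states: "Events should be recorded on the Adverse Event electronic case report form (eCRF"). Section 7.3.1 then adds: "Grade 1 (Mild) AE/SARs are not entered in the electronic CRF in the CCTRN database". The severity table there describes grade 1 as an event without symptoms or with mild ones, seen only as a clinical or diagnostic observation and calling for no intervention. No exception is written for events named in items 1 and 2, and no separate MACE or significant-event form is described.

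**The concern.** The endpoint definition and the data-capture rule do not match. Read literally, items 1 and 2 count a named event whatever its grade, while the capture rule keeps the mildest grade out of the database. The explicit floor on item 3 makes the mismatch harder to dismiss. If grade 2 or higher had been meant throughout, one would expect the qualifier on all three items or in the lead-in sentence.

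This is the primary safety evaluation of a first-in-human trial that injects cells at 20 myocardial sites. Section 9.1.2.3 lists irregular heartbeats among the risks of the injection, and hypersensitivity is a named item 2 event. A mild form of either is information the safety tables would be expected to hold. An event that was not entered cannot be tabulated from the database at analysis.

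**Working it through.** **Step 1. Which named events can be grade 1 under the protocol's own severity table?**

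- Item 1: death is grade 5, and hospitalisation fits grade 3. An HF exacerbation managed without hospitalisation could be grade 1 if symptoms were mild and no intervention was indicated. Item 1 is therefore touched at one edge.
- Item 2: a mild hypersensitivity reaction needing no treatment fits the grade 1 description. So does an asymptomatic VT run seen on post-procedure telemetry (sections 6.1 and 6.5.1) or at ICD interrogation (sections 6.1 and 6.2).

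**Step 2. What other routes into the tables exist?**

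- ICD reports (section 6.2, item 9): local electrophysiology staff review them for reportable clinical events, a term not defined. Copies stay on site, and the sponsor may request them for endpoint adjudication. This is a partial route for VT, and subjects without an ICD do not have it.
- Cancer follow-up (sections 3.2 and 6.5.5): a 12-month records review and an oncology visit look for recurrence. They do not address VT or hypersensitivity.
- Ancillary forms (section 9.5.5): mentioned, but their content is not described.
- Section 7.2.1 says when an abnormal test result must be reported as an adverse event. It does not lift the grade 1 rule.

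No section says how a finding from these routes enters the tables of section 8.3.2.1.

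**Step 3. How sensitive is the planned test to one missing event?** The plan gives no event rates and no share of events expected to be grade 1, so there is no figure of its own to reproduce. The counts below are assumed, for illustration. Inputs from the plan are 15 per arm (Executive Summary), Fisher's exact test (section 8.3.2.1) and the nominal 0.05 level (section 8.6). Sidedness is not stated; two-sided is assumed.

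With equal arms of 15 and all events in one arm, p = 2 × C(15,k) / C(30,k):

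- k = 5: 2 × 3003 / 142506 = 0.042
- k = 4: 2 × 1365 / 27405 = 0.100

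Other assumed counts:

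| Arms | Full count | p | One event fewer | p |
|---|---|---|---|---|
| 15 v 15 | 7 v 1 | 0.035 | 6 v 1 | 0.080 |
| 16 v 15 | 5 v 0 | 0.043 | 4 v 0 | 0.101 |
| 21 v 15 | 6 v 0 | 0.030 | 5 v 0 | 0.062 |

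The second row allows for the maximum of 31 randomised subjects. The third adds the six open-label subjects to 15 randomised to cells, as in the total cohort of section 8.3.2. In each row one unrecorded event moves the comparison across 0.05. This shows how small the counts are. It does not estimate how many events would be lost.

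**The case against.** The strongest reply is that item 2 is headed *significant* clinical events. If an observation that calls for no intervention is not significant, grade 1 falls outside item 2 by definition and the conflict disappears. That reading is possible, but the word is neither defined nor tied to a grade, and sites could apply it differently. The reply supports stating the rule; it does not show that one has been stated.

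Two further points narrow the concern, and both stand. The grade 1 rule is worded for AE/SARs, while section 7.3 names SAE/SSARs separately, so serious events are arguably not barred. The rule also applies alike to both arms, and nothing in the documents suggests differential loss.

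A reader might go further and infer that the Adverse Event eCRF is the sole source of endpoint data and that mild named events are certain to be lost. The documents do not say so: ICD reports may go to adjudication and stay on site as source records, and ancillary forms exist.

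A reader might also add incidental neoplasm to the list. It is a weak example. A lesion needing intervention is above grade 1, one needing further work-up must be reported as an adverse event under section 7.2.1, and recurrence is sought separately at 12 months.

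Finally, a reader might want to put a loss of power on the gap. That would need event rates and a grade 1 share that appear nowhere in the plan. Section 3.5 sets no power target for safety, and section 8.6 treats the findings as preliminary.

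**Conclusion.** The gap is real and worth closing. A stated capture rule narrows a primary endpoint whose definition carries no such limit. It bears mainly on item 2, through mild untreated hypersensitivity and asymptomatic VT, and on item 1 possibly through a mild HF exacerbation without hospitalisation. What the documents support is that these occurrences have no stated route into the safety tables. They do not show that such events would all be missed.

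The number affected cannot be derived from the plan. The illustration rests on assumed counts, a two-sided test and arms of about 15. On those terms one event can decide whether a comparison falls below 0.05.

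A reader might also look to exclusion 27, which sets a VT run length, for a missing endpoint threshold. The documents offer it as an eligibility rule with its own qualifiers. Used for scoring, it would leave short silent runs uncounted and would stop counting shorter symptomatic runs that are recorded today.

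**What to change.** In section 7.3.1, add one sentence exempting the events named in section 3.4.1 items 1 and 2 from the grade 1 rule, so that they are entered on the Adverse Event eCRF at any grade. In section 8.3.2.1, tabulate those events by grade, so that a count of grade 2 or higher can also be read.

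The cost is about one line in each section, a few more eCRF entries across roughly 36 subjects, and slightly higher recorded event rates in both arms. If the sponsor did intend items 1 and 2 to start at grade 2, stating that floor in sections 3.4.1 and 8.3.2.1 would also remove the contradiction, but the mild events would then stay out of the tables by design.
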